5.4.3.3 Abortions

Any spontaneous abortion should be classified as a serious adverse event (SAE; as the Sponsor considers spontaneous abortions to be medically significant events), recorded on the Adverse Event eCRF, and reported to the Sponsor immediately (i.e., no more than 24 hours after learning of the event; see Section [5.4.2](#)).

Any induced abortion due to maternal toxicity and/or embryo-fetal toxicity should also be classified as serious adverse event, recorded on the Adverse Event eCRF, and reported to the Sponsor immediately (i.e., no more than 24 hours after learning of the event; see Section [5.4.2](#)).

Elective abortion not associated with toxicity (e.g., induced abortion for personal reasons) does not require expedited reporting but should be reported as outcome of pregnancy on the Clinical Trial Pregnancy Reporting Form.

5.4.3.4 Congenital Anomalies/Birth Defects

Any congenital anomaly/birth defect in a child born to a female patient or female partner of a male patient exposed to study drug should be classified as a serious adverse event, recorded on the Adverse Event eCRF, and reported to the Sponsor immediately (i.e., no more than 24 hours after learning of the event; see Section [5.4.2](#)).

5.4.4 Reporting Requirements for Medical Device Complaints

The Investigator must report all medical device complaints to the Sponsor. The Investigator should document as much information as possible on the Medical Device Complaint including the product number and expiration date. If the medical device complaint results in an adverse event, the adverse event must be reported on the Adverse Event eCRF. If the event is serious, the Adverse Event eCRF must be completed and reported to the Sponsor within 24 hours after learning of the event (see Section [5.4.2](#)).

5.5 FOLLOW-UP OF PATIENTS AFTER ADVERSE EVENTS

5.5.1 Investigator Follow-Up

The Investigator should follow each adverse event until the event has resolved to baseline grade or better, the event is assessed as stable by the Investigator, the patient is lost to follow-up, or the patient withdraws consent. Every effort should be made to follow all serious adverse events considered to be related to study drug or trial-related procedures until a final outcome can be reported.

During the study period, resolution of adverse events (with dates) should be documented on the Adverse Event eCRF and in the patient's medical record to facilitate source data verification. If, after follow-up, return to baseline status or stabilization cannot be established, an explanation should be recorded on the Adverse Event eCRF.

All pregnancies reported during the study should be followed until pregnancy outcome and reported according to the instructions provided in Section [5.4.3](#).

5.5.2 Sponsor Follow-Up

For serious adverse events, non-serious adverse events of special interest, and pregnancies, the Sponsor or a designee may follow up by telephone, fax, electronic mail, and/or a monitoring visit to obtain additional case details and outcome information (e.g., from hospital discharge summaries, consultant reports, autopsy reports) in order to perform an independent medical assessment of the reported case.

5.6 POST-STUDY ADVERSE EVENTS

The Investigator is not required to actively monitor patients for adverse events after the end of the adverse event reporting period (defined as after the last follow-up visit).

If the Investigator becomes aware of any other serious adverse event occurring after the end of the adverse event reporting period, if the event is believed to be related to prior study drug treatment, the event should be reported directly to the Sponsor or its designee, either by faxing or by scanning and emailing the Serious Adverse Event Reporting Form using the fax number or email address provided to investigators.

5.7 EXPEDITED REPORTING TO HEALTH AUTHORITIES, INVESTIGATORS, INSTITUTIONAL REVIEW BOARDS, AND ETHICS COMMITTEES

The Sponsor will promptly evaluate all serious adverse events and non-serious adverse events of special interest against cumulative product experience to identify and expeditiously communicate possible new safety findings to investigators, IRBs, ECs, and applicable Health Authorities based on applicable legislation.

To determine reporting requirements for single adverse event cases, the Sponsor will assess the expectedness of these events using the following reference document:

- [RO7062931 Investigator Brochure](#)

The Sponsor will compare the severity of each event and the cumulative event frequency reported for the study with the severity and frequency reported in the applicable reference document. Reporting requirements will also be based on the Investigator's assessment of causality and seriousness, with allowance for upgrading by the Sponsor as needed.

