1.3.2 Benefit–Risk Assessment

Before initiation of this first-in-human study, no prior clinical experience with RO7062931 existed. The evaluation of the potential risks of treatment and the specific tests, observations, and precautions required for clinical studies with RO7062931 were based on information from non-clinical toxicology and safety pharmacology studies as well as prior experience with other oligonucleotide therapeutics. Safety and tolerability will be carefully assessed, and study subjects (referring to both healthy volunteers and patients in the protocol) will be closely monitored. The [RO7062931 Investigator Brochure](#), Section 6 summarizes the key risk management activities to consider when administering this novel compound to study subjects.

Based on the exposure multiple to the predicted human efficacious dose calculations, and the non-clinical toxicology data, the selected starting-dose of 0.1 mg/kg is considered to be safe (see Section 3.2.1). Equivalent human exposures anticipated from the target dose range between 0.1 and 4 mg/kg of RO7062931 proposed within this study and evaluated under a controlled setting, should provide a better understanding of clinical safety and tolerability to guide future clinical studies. The risks for an individual study subject due to ascending doses of RO7062931 or study-related procedures are considered to be minimal.

The good safety and tolerability observed to date in CHB patients, the preliminary encouraging dose dependent declines in HBsAg levels, and the favorable results from pre-clinical chronic toxicity studies, support an evaluation of RO7062931 treatment at a dose level of up to 4mg/kg/week and for up to 48 weeks treatment duration when administered with standard of care (SoC) therapies. Consistent with current guidelines ([FDA 2018](#)), non-clinical combination studies of RO7062931 with approved SoC therapies (i.e. NUC or PEG-IFN) were not conducted, as available nonclinical data does not suggest a potential for serious synergistic toxicity.

For further information please refer to the latest [RO7062931 Investigator Brochure](#).

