4.4.1.2 Standard of Care (NUC and PEG-IFN)

As NUCs (entecavir, tenofovir alafenamide or tenofovir disoproxil fumarate) are to be used as background SoC therapies, they are classed as non-investigational medicinal product (NIMP). Please see local prescribing information for additional information.

As PEG-IFN is not licensed for use in CHB patients receiving NUC therapy, it is thus classed as an IMP.

PEG-IFN is a clear and colourless to light yellow sterile liquid provided in prefilled syringes for single use. Each prefilled syringe of 0.5 mL solution contains 180 µg peginterferon alfa-2a.

The list of excipients is as follows: sodium chloride, polysorbate 80, benzyl alcohol, sodium acetate, acetic acid, and water for injections.

The packaging and labeling of PEG-IFN will be in accordance with Roche standard and local regulations. Study drug packaging will be overseen by the Roche clinical trial supplies department and bear a label with the identification required by local law, the protocol number, drug identification and dosage. Study drug should be stored under the recommended storage conditions (2 to 8°C, protected from light). For further details, see the packaging label.

Upon arrival of investigational products at the site, site personnel should check them for damage and verify proper identity, quantity, integrity of seals and temperature conditions, and report any deviations or product complaints to the monitor upon discovery.

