Specific guidelines for adjusting the doses of PEG-IFN for adverse event management are provided in Section 5.2.1.3. If PEG-IFN is interrupted or discontinued permanently, patients should continue treatment with RO7062931 and NUC until the end of the treatment period.

For further information on the PEG-IFN, please refer to the latest PEG-IFN Investigator Brochure.

NUC administration

NUC will be administered per local label or as per prescribing information and should be taken in the morning of RO7062931 or RO7062931 and PEG-IFN administration. NUC administration during the study, including the follow-up period, should be captured in the site documentation and eCRF. This information should include information about any missing doses during treatment and follow-up period.

For further information on the NUCs used in this study, please follow local prescribing information.

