5.3.4 Assessment of Causality of Adverse Events

Investigators should use their knowledge of the study subject, the circumstances surrounding the event, and an evaluation of any potential alternative causes to determine whether or not an adverse event is considered to be related to the study drug, indicating "yes" or "no" accordingly. The following guidance should be taken into consideration:

- Temporal relationship of event onset to the initiation of study drug.
- Course of the event, considering especially the effects of dose reduction, discontinuation of study drug.
- Known association of the event with the study drug or with similar treatments.
- Known association of the event with the disease under study.
- Presence of risk factors in the study subject or use of concomitant medications known to increase the occurrence of the event.
- Presence of non-treatment-related factors that are known to be associated with the occurrence of the event.

For study subjects receiving combination therapy, causality will be assessed individually for each protocol mandated therapy.

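### Section 5.7 names only the RO7062931 brochure for expectedness and the frequency comparison, although PEG-IFN is also an IMP with its own causality assessment

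*Combined protocol and SAP*

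**What the plan says.** Section 5.7 starts broadly: "The Sponsor will promptly evaluate all serious adverse events and non-serious adverse events of special interest against cumulative product experience". For reporting requirements it then becomes specific: "To determine reporting requirements for single adverse event cases, the Sponsor will assess the expectedness of these events using the following reference document". The list that follows has one entry, the "RO7062931 Investigator Brochure". A second comparison is made with whichever reference document applies, and the sentence that sets it up begins: "The Sponsor will compare the severity of each event and the cumulative event frequency reported for the study with the severity and frequency reported in". Section 5.7 adds that reporting also depends on the investigator's view of causality and seriousness, and that the Sponsor may upgrade a case.

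On PEG-IFN, Section 4.4.1.2 states: "As PEG-IFN is not licensed for use in CHB patients receiving NUC therapy, it is thus classed as an IMP". Section 4.4.3 has the Sponsor supply it. Section 5.3.4 says that for subjects on combination therapy "causality will be assessed individually for each protocol mandated therapy". A PEG-IFN brochure is in the reference list. Section 4.4.2.1 points to it for product information ("For further information on the PEG-IFN, please refer to the latest PEG-IFN Investigator Brochure") and Section 4.5.2 for concomitant medication. No section assigns it to expectedness.

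**The concern.** Expectedness is a property of a product's own reference document. The protocol asks the investigator to say which product an event is attributed to, then tests every event against the document of one product. For Cohort 10, and for any optional cohort that includes PEG-IFN, the attribution and the reference can belong to different drugs.

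Serious events attributed to PEG-IFN are foreseeable on the protocol's own account. Section 1.1 says the drug carries notable safety and tolerability risks. Section 5.2.1.1 requires every potential drug-induced liver injury to be reported as an SAE, and stopping of PEG-IFN to be considered along with the other drugs. Cohort 10 is uncontrolled, and Section 1.3.2 records that "non-clinical combination studies of RO7062931 with approved SoC therapies (i.e. NUC or PEG-IFN) were not conducted". The correct classification and timely reporting of such cases to authorities, ethics committees and investigators are at stake.

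**Working it through.** The point is textual, and the plan gives no figure to reproduce. The relevant rules, side by side:

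| Step | Section | Unit of assessment |
|---|---|---|
| Status of PEG-IFN | 4.4.1.2, 4.4.3 | A separate IMP, supplied by the Sponsor |
| Causality | 5.3.4 | Each protocol-mandated therapy |
| Expectedness | 5.7 | RO7062931 brochure only |
| Severity and frequency comparison | 5.7 | The applicable document; only one is named |
| Uses of the PEG-IFN brochure | 4.4.2.1, 4.5.2 | Product information and concomitant medication; not expectedness |

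Take a serious event attributed to PEG-IFN alone. There are four cases:

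| Listed in PEG-IFN brochure | Listed in RO7062931 brochure | Result under 5.7 as written | Result against PEG-IFN's own document |
|---|---|---|---|
| Yes | Yes | Expected | Expected |
| No | No | Unexpected | Unexpected |
| Yes | No | Unexpected | Expected |
| No | Yes | Expected | Unexpected |

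The rule goes wrong in the last two rows. The third over-reports. The fourth under-reports, which is the less safe direction. How many events fall in either row cannot be found, because neither brochure's content is in the documents.

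The gap looks like an oversight. Section 5.3.5.11 on overdose was widened to cover IMPs and NIMPs, while the Version 4 summary of changes has no entry for Section 5.7.

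Exposure: Cohort 10 has 8 patients initially and may be expanded to 30 (Section 6.1), with up to 48 weeks of treatment (Section 3.1.1.3) and 24 weeks of follow-up. The documents give no rate of PEG-IFN-related serious events. As an illustration only, assume a per-patient probability p and independent patients. The chance of at least one such event among n patients is 1 − (1 − p)^n:

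| Assumed p | n = 8 | n = 30 |
|---|---|---|
| 1% | 1 − 0.99^8 = 7.7% | 1 − 0.99^30 = 26.0% |
| 2% | 1 − 0.98^8 = 14.9% | 1 − 0.98^30 = 45.5% |
| 5% | 1 − 0.95^8 = 33.7% | 1 − 0.95^30 = 78.5% |
| 10% | 1 − 0.90^8 = 57.0% | 1 − 0.90^30 = 95.8% |

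These are chances that the rule is ever applied to a PEG-IFN event. They are not chances of misclassification, which also needs the two brochures to differ on that event.

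**The case against.** The best defence is that Section 5.7 is incomplete rather than prohibitive. It refers to accumulated product experience, to whichever reference document applies and to applicable legislation, and it allows upgrading by the Sponsor. A safety group could use the PEG-IFN brochure in practice. This softens the consequence but does not repair the text: only one document is named, so nothing in the section tells the reader that another applies.

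It can also be said that the likelier error is conservative, since an event known only for PEG-IFN would be over-reported. The documents give no example of the under-reporting case, and Section 1.2.2 reports no severe or serious events in Parts 2a and 2b at the cut-off. That is fair on likelihood. But those parts did not test the PEG-IFN combination, and a reporting rule should not depend on errors falling the safe way.

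Four stronger readings are tempting, and the documents do not support them:

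- A reader might infer that PEG-IFN events are in fact misclassified. That needs the two brochures' contents, which are not available.
- A reader might infer that the trial has no reference for PEG-IFN safety. Section 3.2.3 plans a qualitative comparison of Part 2c with Part 2a/2b placebo data and with historical experience of standard-of-care drugs, which include PEG-IFN. Only the comparison within Section 5.7 lacks a source.
- A reader might infer that the plan cannot show whether RO7062931 worsens PEG-IFN toxicity, or that over-reporting would swamp the signal. The first question belongs to Section 3.2.3, the safety analyses in 6.5 and the data review in 3.1.2, not to single-case expectedness. The second has no figure behind it. Section 1.3.2 also gives a reason for omitting combination studies: the cited guidance, and non-clinical data that did not suggest serious synergistic toxicity.
- A reader might extend the point to the NUCs. They are NIMPs, and no NUC problem is shown.

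**Conclusion.** The concern holds as an internal inconsistency in the safety-reporting rule. Causality is assessed per product and PEG-IFN is an IMP, yet expectedness and the severity and frequency comparison in Section 5.7 rest on the RO7062931 brochure alone. Serious events attributed to PEG-IFN can therefore be misclassified in either direction, and the Section 5.7 frequency comparison has no PEG-IFN source.

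The reach is limited to Cohort 10 and any Cohort 11 or 12 that includes PEG-IFN. The number of events affected cannot be estimated from the documents. The conclusion assumes that Section 5.7 is followed as written, and that at least some events are listed in one brochure and not the other. It should be corrected, but it does not bear on sample size, the efficacy analysis or how patients are treated.

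**What to change.** In Section 5.7, replace the single entry with a list by IMP: the RO7062931 Investigator Brochure for events attributed to RO7062931, and the PEG-IFN Investigator Brochure for events attributed to PEG-IFN. State that expectedness, and the severity and frequency comparison, are made against the document of each IMP to which causality is assigned under Section 5.3.4, so that an event attributed to both is checked against both.

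The cost is a few lines of protocol text and the matching change to the safety-reporting set-up. The protocol already cites the PEG-IFN brochure, and the change needs no new data collection.

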6. STATISTICAL CONSIDERATIONS AND ANALYSIS PLAN

Statistical summaries will be descriptive in nature and will be reported separately for each part of the study within the clinical study report. All study subjects who are randomized to receive placebo in Part 1 will be pooled as a respective placebo control group for Part 1. Placebo from Part 2b will be pooled with the placebo cohort from Part 2a.

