Descriptive statistics will be used to summarize the viral dynamic response outcome measure of quantitative HBsAg (log₁₀), actual and change from baseline in quantitative HBsAg at each time-point by dose group. Rate of decrease in quantitative HBsAg will also be summarized using descriptive statistics.

PK/Viral Dynamic Response Analyses

The relationship between RO7062931 and dose, and metabolite(s) and dose if applicable, and the change of HBsAg at each time-point and rate of decrease will be explored by graphical analysis. The relationship between RO7062931 PK and urinary parameters and HBsAg will also be explored. An appropriate exposure/dose-response model may be fitted to the data from Part 2a. This model may be used to guide dose selection for Part 2b, *and will be further developed with data from Parts 2b and 2c.*

PHARMACOKINETIC ANALYSES

Pharmacokinetic parameters as defined will be determined using standard non-compartmental methods for both RO7062931 and any metabolite(s) when available. Descriptive statistics of urine PK parameters for RO7062931 and any metabolite(s) will be presented, where available. PK and PD data from this study may be used to develop a population PK/PD model.

Where appropriate, listings and summary tables of nucleoside/nucleotide-analogues, tenofovir, tenofovir alafenamide, entecavir, adefovir, or telbivudine concentrations will be provided based on the sparse sampling throughout the study.

Study subjects will be excluded from the pharmacokinetic analysis population if they significantly violate the eligibility criteria or the protocol, or if data are unavailable or incomplete which may influence the pharmacokinetic analysis.

SAFETY ANALYSES

All study subjects who receive at least one dose of study drug will be included in the safety analysis. The safety endpoints include, but may not be limited to, incidence of adverse events (including injection site reactions [ISRs]), treatment discontinuations due to adverse events, change from baseline by time in laboratory parameters and incidence of clinically significant laboratory abnormalities, change from baseline by time of ECG parameters and abnormalities, and vital signs and abnormalities.

OTHER ANALYSES

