3. STUDY DESIGN

3.1 DESCRIPTION OF STUDY

3.1.1 Overview of Study Design

The study will be conducted in two parts, of which Part 1 will be in healthy volunteers and Part 2 will be in CHB patients (see Figure 1). Both parts of the study are randomized. Part 1 will evaluate the safety, tolerability and PK of RO7062931, and if applicable metabolite(s), following SC administration of single doses in healthy volunteers. Part 2 will evaluate the safety, tolerability PK and PD (viral dynamics) following administration of multiple SC doses of RO7062931 in CHB patients *over a short treatment duration* (Figure 1) and *extended treatment durations* (Figure 2) (see Section 4.6).

Figure 1 Study Design: Parts 1, 2a, and 2b Short Treatment Durations

[figure not shown]
[figure not shown]

Figure 2 Study Design: Part 2c - Extended Treatment Durations

The total duration of the study for each HV in Part 1 will be ≥ 16 weeks.

- Part 1 (1 dose)
 - Screening: Up to 28 days;
 - In Clinic period: Days – 1 to 3;
 - Safety Follow-up: up to at least Day 85.

The total duration of the study for each patient in Part 2 will be ≥ 24 weeks, *except for Part 2c where the total duration may be ≥ 52 weeks.*

- Part 2a (2 doses, Q1M)
 - Screening: Up to 56 days;
 - In Clinic period (optional): Days – 1 to 2 and Days 29 to 30;
 - Safety Follow-up: up to at least Day 113.
- Part 2b (3 doses, Q2W)
 - Screening: Up to 56 days;
 - In Clinic period (optional): Days – 1 to 2 and Days 29 to 30;
 - Safety Follow-up: Up to at least Day 113.
- Part 2b (4 doses, QW)
 - Screening: Up to 56 days;
 - In Clinic period (optional): Days –1 to 2 and Days 22 to 23;
 - Safety Follow-up: Up to at least Day 106.

- Part 2b (5 doses, QW)
 - Screening: Up to 56 days;
 - In Clinic period (optional): Days – 1 to 2 and Days 29 to 30;
 - Safety Follow-up: Up to at least Day 113.
- Part 2c (QW)
 - Screening: Up to 28 days;
 - Treatment period: Up to 48 weeks;
 - Follow-up period: Up to 24 weeks.

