3.1.1.2 Part 2a/2b: Proof-of-Mechanism in CHB Infected Patients

Part 2a/b is a multi-center randomized, Sponsor-open, Investigator-blinded, subject-blinded, placebo-controlled, adaptive, parallel multiple-dose study in chronically HBV infected patients, with the aim to study the safety, tolerability, PK of RO7062931 (and if applicable metabolite[s]), and the relationship between RO7062931 dose, dose regimen and viral dynamic response.

In Part 2a, CHB patients will receive two monthly doses (Q1M) of RO7062931. Part 2a is planned to consist of 4 parallel cohorts of 3 RO7062931 dose levels and one placebo.

In addition to safety, PK will be evaluated in the first two patients of each dose cohort prior to subsequent randomization to confirm that RO7062931 exposure is comparable as found for the HVs. Cohort doses may be adjusted across the patient cohorts if plasma PK appears to significantly differ from the HVs. Each cohort in Part 2a will consist of 6 patients.

In Part 2b, a dose identified from the dose-response analysis of Part 2a (based on either HBsAg decline or maximum dose evaluated and well tolerated) will be tested in different dosing regimens administered weekly (QW) or bi-weekly (Q2W). The total dose of 400 mg per day will not be exceeded. The selection of dosing regimens will be guided by the analysis of safety, PK and PD data of all previous cohorts in Part 2.

In Part 2b, each patient will be randomized to active or placebo in each dose cohort/level in a 3:1 ratio. Each cohort in Part 2b will be comprised of 8 patients, six patients will receive RO7062931 and two will receive placebo. CHB patients will be followed up weekly for the first 28 days and then monthly up to at least 84 days after the last dose of RO7062931.

There will be two optional overnight stay periods for the patients: between Day –1 and Day 2, and between Day 29 and Day 30 (exception: between Day 22 and Day 23 for the cohort with 4 doses given QW). If the Investigator agrees, the patients can leave the clinic after completing the last evening assessment and return the following morning prior to the first scheduled assessment. In Part 2b, where drug administration is given on days other than Day 1 and Day 29 (or Day 22 for the cohort with 4 doses given QW), the patients will be administered the drug in the clinic as an ambulatory visit.

Visits and assessments will be performed as indicated in the SoA tables (see [Appendix 3](#) to [Appendix 14](#)).

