Patients will be randomized to placebo or one of three active dose levels of RO7062931 in a 1:1:1:1 ratio. The randomization numbers will be generated by an IxRS (Interactive voice/web response system) according to specifications provided by the sponsor to the external randomization vendor. The Sponsor may postpone or stop enrolment of certain patient subgroups, in order to evaluate pharmacodynamic parameters in different patient subgroups. Each cohort/arm will consist of 6 patients. These cohorts will be run in parallel. The treatment allocation will be managed by the unblinded

Pharmacist and will be based on the IxRS randomization assignment. The unblinded pharmacist will fix tape to the syringes to mask any potential color difference between syringes while still allowing visualization of dose volumes.

The PK data from the first 8 patients of Part 2a (assuming 2 patients per cohort/arm), who have been randomized and have received their first dose will be reviewed by the project Clinical Pharmacologist prior to randomization of any further patients to ensure the exposure for patients is in the same range as for healthy volunteers. Should the ranges look different, dose levels for subsequent patients may be adjusted.

Part 2b

Similar to Part 1, each patient will be randomized to active treatment or placebo in each dose cohort/level in a 3:1 ratio. The randomization numbers will be generated by an IxRS (Interactive voice/web response system) according to specifications provided by the sponsor to the external randomization vendor. The Sponsor may postpone or stop enrolment of or only enroll certain patient subgroups, in order to evaluate pharmacodynamic parameters in different patient subgroups. Each cohort will be comprised of 8 patients, six patients will receive RO7062931 and two will receive placebo. The first two cohorts will be run in parallel; therefore, patients will also be randomized to a cohort. Any subsequent cohorts may be sequential or parallel. The treatment allocation will be managed by the unblinded Pharmacist and will be based on the IxRS randomization assignment. The method of tape masking as described for Part 2a will be used in Part 2b to protect the blind.

Part 2c

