5.3.5.1 Diagnosis versus Signs and Symptoms

Injection-Site Reactions

Adverse events that occur during or after study drug administration and are judged to be local and related to the SC study drug injection should be captured as a diagnosis (e.g., "injection site reaction" on the Adverse Event eCRF. If possible, avoid ambiguous terms such as "systemic reaction.") Associated signs and symptoms should be recorded on the dedicated Injection Reaction eCRF.

Grading of pre-defined injection site reaction symptoms is described in [Appendix 17](#). If a patient experiences both a local and systemic reaction to the same dose of study drug, each reaction should be recorded separately on the Adverse Event eCRF, with signs and symptoms also recorded separately on the dedicated Injection Reaction eCRF.

Other Adverse Events

For adverse events, a diagnosis (if known) should be recorded on the Adverse Event eCRF rather than individual signs and symptoms (e.g., record only liver failure or hepatitis rather than jaundice, asterixis, and elevated transaminases). However, if a constellation of signs and/or symptoms cannot be medically characterized as a single diagnosis or syndrome at the time of reporting, each individual event should be recorded on the Adverse Event eCRF. If a diagnosis is subsequently established, all previously reported adverse events based on signs and symptoms should be nullified and replaced by one adverse event report based on the single diagnosis, with a starting date that corresponds to the starting date of the first symptom of the eventual diagnosis.

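### Placebo patients with 2 to 5 planned injections form one control, so per-patient injection-site-reaction incidence can differ from placebo by dosing frequency with no drug effect; a per-injection measure should be added

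*Combined protocol and SAP*

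**What the plan says.** Section 6 gives the control group for Parts 2a and 2b in one sentence: "Placebo from Part 2b will be pooled with the placebo cohort from Part 2a". The synopsis (Statistical Methods) repeats it. Neither place mentions regimen or number of injections.

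The make-up of the pool follows from the design:

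- **Part 2a.** Section 4.3: "Patients will be randomized to placebo or one of three active dose levels of RO7062931 in a 1:1:1:1 ratio" and "Each cohort/arm will consist of 6 patients". Section 3.1.1.2: "In Part 2a, CHB patients will receive two monthly doses (Q1M) of RO7062931".
- **Part 2b.** Section 4.3: "Each cohort will be comprised of 8 patients, six patients will receive RO7062931 and two will receive placebo". Section 3.1.1 lists three schedules: 3 doses every two weeks, 4 doses weekly and 5 doses weekly.

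The synopsis (Safety Analyses) lists among the safety endpoints "incidence of adverse events (including injection site reactions [ISRs", and Section 6.5.1 plans listings and frequency tables. No rate per injection is mentioned. On data capture, Section 5.3.5.1 says: "Associated signs and symptoms should be recorded on the dedicated Injection Reaction eCRF".

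There are two follow-up calendars. The 4-dose cohort has its last dose on Day 22 and the entry "Safety Follow-up: Up to at least Day 106" in Section 3.1.1. The 2-, 3- and 5-dose regimens have their last dose on Day 29 and are followed to at least Day 113. Section 6.6.1 summarises HBsAg at each time-point without saying whether that means study day or time since last dose.

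**The concern.** A patient who receives 5 injections has more opportunities for at least one reaction than a patient who receives 2, whatever is in the syringe. Half of the planned pool comes from the 2-injection schedule. Comparing a regimen's per-patient incidence with the pool therefore mixes any drug effect with the difference in number of injections.

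This bears on a primary objective: Section 2.1 asks for safety and tolerability relative to placebo after multiple doses in patients. Severe ISRs are events of special interest (Section 5.1.3), and Part 2b exists to compare dosing frequencies, which is the factor that drives the offset. A reader of the final tables could take a higher ISR percentage on weekly dosing as a local effect of the drug, or a lower one on monthly dosing as reassurance.

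A second, smaller matter is the visit calendar. If tables are keyed to study day, the two calendars do not line up after Day 50, and the placebo pool splits at late visits.

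**Working it through.** **Reproducing the planned counts.** Part 2b: 8 x 1/4 = 2 placebo and 6 active per cohort, as Section 4.3 states. Part 2a: 4 x 6 = 24 patients, 6 on placebo. With one cohort per Part 2b schedule, the pool is 6 + 2 + 2 + 2 = 12. Mean injections = (6x2 + 2x3 + 2x4 + 2x5)/12 = 36/12 = 3.0.

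**Offset with no drug effect.** Let p be the risk of a reaction at one injection, equal on drug and placebo. The documents give no value, so p is an assumption, shown over a range. With independent injections, the expected proportion of patients with at least one reaction after k injections is f(k) = 1 - (1-p)^k. The pool is [6f(2) + 2f(3) + 2f(4) + 2f(5)]/12. At p = 10%: (6x0.190 + 2x0.271 + 2x0.344 + 2x0.410)/12 = 26.6%.

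Expected incidence in %, with the difference from the pool in points (taken before rounding):

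| p | Pool | 2 doses | 3 doses | 4 doses | 5 doses |
|---|---|---|---|---|---|
| 2% | 5.9 | 4.0 (-1.9) | 5.9 (0.0) | 7.8 (+1.9) | 9.6 (+3.8) |
| 5% | 14.1 | 9.8 (-4.4) | 14.3 (+0.1) | 18.5 (+4.4) | 22.6 (+8.5) |
| 10% | 26.6 | 19.0 (-7.6) | 27.1 (+0.5) | 34.4 (+7.8) | 41.0 (+14.4) |
| 20% | 47.2 | 36.0 (-11.2) | 48.8 (+1.6) | 59.0 (+11.9) | 67.2 (+20.1) |
| 30% | 63.0 | 51.0 (-12.0) | 65.7 (+2.7) | 76.0 (+13.0) | 83.2 (+20.2) |

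**Within-patient correlation.** Some patients may react repeatedly and others never. Under a beta-binomial model with correlation rho, a = p(1-rho)/rho and b = (1-p)(1-rho)/rho, the chance of no reaction in k injections is the product of (b+i)/(a+b+i) over i = 0 to k-1. At p = 10%:

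| rho | Pool | 2 doses | 5 doses |
|---|---|---|---|
| 0 | 26.6 | 19.0 (-7.6) | 41.0 (+14.4) |
| 0.3 | 20.2 | 16.3 (-3.9) | 27.1 (+6.9) |
| 0.6 | 15.4 | 13.6 (-1.8) | 18.5 (+3.1) |
| 0.9 | 11.3 | 10.9 (-0.4) | 11.9 (+0.6) |

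The direction stays the same; the size falls towards zero.

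**Sampling noise.** At p = 10% with independence, the variance of the 5-dose difference (6 active, 12 placebo) is 0.4095x0.5905/6 plus the sum of n(k)f(k)(1-f(k)) divided by 12 squared. That is 0.0403 + 2.2534/144 = 0.0403 + 0.0156 = 0.0560, so the standard error is about 24 points.

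**Per-injection measure.** The expected number of reactions divided by injections is p in every regimen and in the pool, whatever rho is, provided p does not change with injection number. The offset under no drug effect is zero.

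**Visits.** Planned placebo patients by study day, quantitative HBsAg (Appendices 3, 5, 7 and 9): 12 through Day 50; 10 on Days 57, 85 and 113; 2 on Days 78 and 106. For hematology, chemistry and coagulation, Day 50 also has only 2. By days since last dose:

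- 4-dose cohort: Days 29, 36, 43, 50, 78, 106 minus 22 = +7, +14, +21, +28, +56, +84.
- Other regimens: Days 36, 43, 50, 57, 85, 113 minus 29 = +7, +14, +21, +28, +56, +84.

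The calendars then coincide, and all 12 contribute wherever the assessment is scheduled.

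**The case against.** The strongest reply is that this is a small descriptive study and the plan excludes nothing. Section 6 calls the summaries descriptive. The synopsis list of safety endpoints is explicitly open, and no denominator is fixed for the frequency tables. Recurrent events are recorded separately (Section 5.3.5.3) and study drug administration is listed (Section 6.4), so a per-injection view is available. Per-patient incidence is a fair measure of the burden of a regimen. Regimen-matched placebo would be 2 patients per Part 2b cohort, which is uninformative, so pooling is sensible. The written decision rules do not use this comparison: the stopping rule counts patients within an arm (Section 3.1.3.1), and Part 2b selection rests on HBsAg decline and dose-limiting events (Sections 6.10.1.2 and 6.10.1.3). The preliminary data in Section 1.2.2 report no regimen-dependent rise in adverse events overall.

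Most of this stands, and it limits the point. It does not remove it: the plan names no exposure-adjusted measure for a comparison with placebo that is a primary objective, and small arms add noise to a systematic offset without cancelling it.

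A reader might infer four stronger things that the documents do not support:

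- *That the tables will show a false gradient.* No ISR rate is given; the offset depends on a non-zero shared risk and imperfect correlation.
- *That the error is +8 to +14 points for weekly dosing.* That is the 5-dose result for assumed risks of 5% and 10% with independent injections, and correlation reduces it.
- *That pooling creates the gradient.* Injection counts create it.
- *That late visits of the 4-dose cohort have only 2 placebo patients.* That follows only if tables are keyed to study day, which Section 6.6.1 does not say. Section 3.1.2 already pairs Day 57 with Day 50 for the 4-dose cohort, which points to alignment on last dose.

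**Conclusion.** The point holds in a conditional form. With a shared non-zero per-injection risk and imperfect within-patient correlation, per-patient ISR incidence against this pool is offset in a known direction: upwards for 4 and 5 weekly doses, downwards for 2 monthly doses, and close to zero for 3 doses. For assumed risks of 2% to 30% and independent injections, the range is about +4 to +20 points at 5 doses and -2 to -12 points at 2 doses, falling towards zero with correlation. Against a standard error of about 24 points (5 doses, p = 10%), the offset would rarely be visible in one table, and no planned test or written decision rule is invalidated.

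The figures assume one cohort per Part 2b schedule, placebo dosed on the same days as active, and one injection per dosing occasion. They use planned numbers: Section 1.2.2 reports 27 patients in three Part 2b cohorts against 24 planned, so actual placebo counts may differ slightly.

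The visit question is missing detail, secondary to the ISR measure.

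**What to change.** 1. Keep the pooled placebo group.
2. In Sections 6.5 and 6.5.1, name ISRs per injection given as the measure for comparing regimens with placebo: reactions divided by injections administered, each reaction assigned to the injection it follows, with the patient as the cluster if an interval is shown. With 6 patients per arm, any interval is indicative only.
3. Show per-patient ISR incidence by number of injections received, active and placebo, as a supporting table.
4. State that follow-up visits in the Part 2a/2b summaries are presented by days since last dose (+7, +14, +21, +28, +56, +84). Apply this to the whole follow-up period; remapping only the later visits would leave the 4-dose cohort with gaps. The Day 29 HBsAg modelling in Section 6.10.1.3 is defined on study day and can stay so.

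The cost is SAP wording and one or two extra tables. The Injection Reaction and Adverse Event eCRFs and the dosing records already hold the data, and trial conduct does not change.
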